3.0 Intervention to be studied (if applicable)

The intervention we are studying is transcutaneous auricular vagus nerve stimulation (taVNS) which is simply electrical nerve stimulation administered at the ear which targets the auricular branch of the vagus nerve. In this study, taVNS will be administered using the Spark Sparrow Ascent System which is a non-significant risk

investigational device. The Spark Sparrow Ascent System is based on an FDA-cleared device provided by Spark Biomedical and has completed all safety and compliance testing. taVNS is a non-significant risk method that has been approved by the MUSC IRB for many ongoing taVNS trials. [name] are the PI or Co-I of more than seven ongoing taVNS trials. The Spark device summary has been uploaded to the MUSC IRB portal.

In this study, we will use the device as an anti-pain device in participants with chronic post-stroke upper extremity pain. Participants will be randomized to receive 30-minute active taVNS (tragus and cymba conchae) or sham taVNS (earlobe) during their in-person visit. In prior studies in our laboratory, we demonstrated that taVNS can be safely and feasibly administered in chronic stroke populations ([name] et al., 2023, [name] et al., 2023).

4.0 Study Endpoints (if applicable)

Primary Outcome: *Safety and Feasibility*

The main outcomes of this pilot trial will be the safety and feasibility of implementing taVNS in the population with chronic post-stroke upper extremity pain.

Secondary Outcomes: *Quantitative Sensory Testing (QST)*

We will systematically determine information about A β (sensory), A δ (pain), and C (pain tolerance) fiber activity with a 30 \times 30 mm thermode attached to the non-affected forearm (left arm) of participants (TSA2 thermode; Medoc, Durham, NC, USA). Using the TSA2, we will determine heat sensory, pain, and tolerance thresholds using the method of limits, beginning at 32°C and increasing by 0.5°C per second. Participants will be asked to press a button (to record temperatures) when the stimulus is first detected (sensory threshold), when it becomes painful (pain threshold), and then when the stimulus is intolerable (pain tolerance). When ‘intolerable’ is indicated, the thermode ceases heating and quickly returns to 32°C. This is repeated for 5 trials to obtain average sensory, pain, and tolerance thresholds. We will acquire QST data before and after the 30-minute taVNS. We will explore the analgesic effects by comparing the pre- and post-intervention QST ratings.

Secondary Outcomes: *Subjective Pain Ratings*

Participants will rate their post-stroke upper extremity pain intensity before and after the taVNS using a standard numeric pain rating scale (0-10). We anticipate participants will rate lower pain intensity post-intervention.

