1.0 Objectives / Specific Aims

In this study, our main goal is to establish transcutaneous auricular vagus nerve stimulation (taVNS) as an effective non-invasive neuromodulation method for analgesia of post-stroke upper extremity pain.

We will recruit up to 20 participants with chronic post-stroke upper extremity pain from the greater Charleston area using MUSC COBRE resources. Participants are required to have an ischemic or hemorrhagic stroke that occurred at least 6 months prior and are currently suffering upper extremity pain. Each participant will undergo an in-person visit to our lab at MUSC [name]. They will first finish the pain questionnaires and have quantitative sensory testing (QST) conducted to determine baseline pain thresholds. Participants will then receive 30 minutes of taVNS (either active or sham). Upon the completion of the stimulation intervention, they will then be tested for another QST and pain questionnaires. All research is being done at MUSC [name] Center for Biomedical Imaging.

Aim 1: Test the safety and feasibility of taVNS in participants with chronic post-stroke upper extremity pain.

Over the last 8 years, our group has demonstrated that taVNS is safe and feasible in several different populations in our previous studies. Specifically, we have demonstrated that taVNS is well tolerated and safe for participants with chronic stroke in our previous clinical trial ([name] et al., 2023, [name] et al., 2023). In this study, we will further verify the safety and feasibility of taVNS in the population with chronic post-stroke upper extremity pain.

Aim 2: Investigate whether taVNS can modulate pain in this population compared to sham.

In this single-visit, single-blinded, sham-controlled pilot trial, we will compare changes in post-stroke upper extremity pain scores and pain threshold derived from QST before and after a 30-minute taVNS intervention, as well as between active and sham taVNS. The findings will help us understand whether taVNS can modulate pain in this population.

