5.0 Inclusion and Exclusion Criteria/ Study Population

Twenty participants with upper extremity post-stroke pain of all ethnic and racial categories will be accepted into this study protocol. No preference will be given based on race, gender, or ethnicity. Pregnant females and children under the age of 18 will be excluded for safety reasons.

Inclusion Criteria:

- Age 18-80
- Have the capacity and ability to provide one’s own consent in English and sign the informed consent document.
- Ischemic or hemorrhagic stroke that occurred at least 6 months prior
- Unilateral stroke lesions in the left hemisphere
- Right upper extremity pain

Exclusion Criteria:

- Primary intracerebral hematoma or subarachnoid hemorrhage
- Documented history of dementia

- Documented history of uncontrolled depression or psychiatric disorder
- Uncontrolled hypertension despite treatment, specifically SBP (Systolic Blood Pressure) / DBP (Diastolic Blood Pressure) $\geq 180/100$ mmHg
- Pregnancy

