10.0 Study Design / Methods

Study Overview:

After determining eligibility and interest, written informed consent will be obtained from participants at the MUSC Center for Biomedical Imaging. After consent is obtained, the participants will then complete a pregnancy test and conduct a brief daily life functioning battery. Enrolled participants will start the experiment. They will first finish the subjective pain rating and have quantitative sensory testing (QST) conducted to determine baseline pain thresholds. Participants will then receive 30 minutes of tVNS (either active or sham). Upon the completion of the stimulation intervention, they will then be tested for another subjective pain rating and QST. The timeline of the experiment and group assignment overview are displayed below.

Experiment Overview – Investigate the anti-pain effect of taVNS in chronic post-stroke upper extremity pain

Recruitment, Screening, and Consent Procedures:

Recruitment will be conducted by the study team utilizing the MUSC RESTORE list to identify and contact prospective chronic stroke patients. Participants who are found to be appropriate candidates will be offered to be phone screened and educated regarding the study's details. If interested in participating in the study, they will be consented and enrolled into the study's protocol. Additionally, RESTORE staff can also give rack cards to interested RESTORE (stroke registry) individuals. If interested in participating in the study, they will be consented and enrolled into the study's protocol.

Daily Life Function Battery:

All participants will complete a daily life function battery after being enrolled. This battery includes the following questionnaires in specific life domains that will be used to identify baseline characteristics of individuals: Demographics; Pain Screening; Substance Use: TAPS; Pain Intensity & Interference: PEG; Physical Functioning/QDL: PROMIS Physical Functioning 6b; Sleep: PROMIS Sleep Disturbance 6a; Sleep: Sleep Duration; Depression: PHQ9; Anxiety: GAD7.

Pregnancy Test Procedures:

If participants are a person of childbearing age, they will be provided with a pregnancy test strip. After completing the pregnancy test, participants with negative results will be asked to continue to the remaining study procedures, whereas those with a positive result will be debriefed and released.

Subjective Pain Rating:

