channels of stimulation (auricular vagus, auricular trigeminal, and both). Two individual stimulation frequencies will be set: 15 Hz at cymba concha and 100 Hz adjacently anterior to tragus. The pulse duration will be set to 250 μ s for all participants. The stimulation intensities delivered (in mA) will be a standardized 2X Perceptual Threshold. This means that all individuals will first have a perceptual threshold conducted, during which incremental increases and decreases in current intensity will be applied until the participant barely feels the stimulation. That is considered the perceptual threshold. All stimulation then will be delivered at 2X this value. Perceptual threshold will be conducted at the beginning of the taVNS intervention. This is how we have conducted stimulation at MUSC in prior IRB-approved studies which have been safe and rated comfortable and not painful. Sham stimulation will be administered at identical parameters of cymba concha, however, the electrodes will be attached to the earlobe, which is not believed to have a high density of cranial nerve innervation. If the participant states that the stimulation intensity is discomforting or imperceivable in any of the stimulation groups, the researcher will gradually decrease until a comfortable stimulation intensity is achieved. The taVNS session will last for 30 minutes.

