12.0 Data Management

All data will be stored in the Redcap database as well as in paper documentation. Information about the participants (including their identifiable private information) may have all their identifiers removed and used for future research studies or distributed to other researchers for future research without additional informed consent. After participation, RedCAP data will be downloaded in Excel format to the secure MUSC server. Paper documentation will be stored in locked cabinet within a locked office of the study team. In terms of publication, data will be published in aggregate form, so individual participants will not be identifiable in the final manuscript. No identifying information will be published.

Confidentiality and Quality Control: All study personnel will complete Social-Behavioral-Educational research CITI training, and also complete in-lab training regarding data security practices. Study personnel will be trained in the IRB protocol. The investigator, and co-investigators will be available to monitor data collection to ensure quality, confidentiality, and adherence to the IRB protocol.

All study's procedures will take place at the MUSC [name] Neuroimaging Center. Regarding documentation, participant names will appear only on the IRB-approved Consent and HIPAA.

The RESTORE registry (Pro#00037803), from which this study will recruit subjects, also serves as a data analysis tool by which interdisciplinary teams may share data across projects and provide MUSC's stroke recovery research community with a more complete registry with key stroke elements. Some subjects may have participated or will participate in other stroke related research studies at MUSC. Sharing data from this and other stroke research studies with RESTORE will allow for more targeted recruitment efforts in the future and could reduce the burden placed on subjects by reducing the duplicative efforts of collecting common data and physical function assessments requested by multiple studies and storing them in one centralized and secure location. The third Aim of this study leverages this ability, as other studies will be better able to target their recruitment based on the information collected in these assessments. De-identified information/data will only be shared once study is completed.

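### Section 4.0 makes safety the primary outcome without a variable, instrument or time point, and the visit text shown has no standard adverse-event query, so a low count or an arm difference may partly reflect how events were asked about

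*Protocol*

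**What the plan says.** Section 1.0 sets the first aim: "Aim 1: Test the safety and feasibility of taVNS in participants with chronic post-stroke upper extremity pain". Section 4.0 carries it into the primary outcome: "The main outcomes of this pilot trial will be the safety and feasibility of implementing taVNS". Neither section says which events count, how or when they are sought, or what will be counted. In the same Section 4.0, QST has a device, a heating rate, five trials and pre/post timing, and the pain rating has a 0-10 scale and pre/post timing.

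The design is a single visit, single-blinded by Section 1.0. Section 3.0 gives the arms: "Participants will be randomized to receive 30-minute active taVNS (tragus and cymba conchae) or sham taVNS (earlobe". For the period after stimulation, Section 10.0 says: "Upon the completion of the stimulation intervention, they will then be tested for another subjective pain rating and QST".

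Safety text appears in four other places:

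- Section 10.0 lowers the intensity on a participant's statement: "If the participant states that the stimulation intensity is discomforting or imperceivable in any of the stimulation groups".
- Section 13.0 has any adverse event reported to the IRB within 48 hours, and says none is expected.
- Section 14.0 says the session will be monitored and allows the other ear to be tried if the ear becomes painful.
- Section 15.0 lists the risks, has staff watch for burns by talking with participants, and says the team will assess a heart-rate or blood-pressure change if one occurs.

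The only blood-pressure threshold is the one attached to the exclusion criterion in Section 5.0: "Uncontrolled hypertension despite treatment".

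**The concern.** A safety outcome is only as informative as the way events are sought. When some events are found because a participant volunteers them and others because a staff member happens to ask, the count mixes the event rate with the amount of questioning. A zero or low count is then hard to read, and it is the result the trial would report under its first aim.

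The comparison between arms is exposed too. The electrodes sit at visibly different sites, so staff who attach them could know the allocation, and informal questioning could differ between active and sham without anyone intending it.

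This cannot be left to an analysis plan. Such a plan can choose the summary statistic, but it cannot recover answers or readings that the visit did not collect.

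**Working it through.** The protocol gives no figure for the safety outcome (no target rate, precision or justification of the sample size), so there is nothing to reproduce. The check is mainly a comparison of sections, followed by a short illustration.

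**Step 1. Section 15.0 risks against the capture described in the text shown.**

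| Risk in Section 15.0 | Specific check described | General provision |
|---|---|---|
| Burn | Talking with the participant | Session monitoring (14.0) |
| Local discomfort | Intensity lowered if the participant says so (10.0) | Session monitoring |
| Soreness, numbness | None | Session monitoring |
| Headache, dizziness, facial pain | None | Session monitoring |
| Fainting | None, but plainly visible | Session monitoring |
| Slowed heart rate, lowered blood pressure | No measurement described | Session monitoring, which may miss a change without symptoms |

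No row has a fixed question, a recording form or a stated time of asking. The 48-hour rule in Section 13.0 applies to every row, but it governs the reporting of events already known, not how they are found.

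**Step 2. Internal mismatch.** Section 15.0 sets out what the team will do if heart rate or blood pressure changes. The visit procedures in Section 10.0 describe no reading of either that would reveal a change. The same paragraph speaks of several sessions, although Section 1.0 describes one visit, so this text is not fully matched to the present design.

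**Step 3. Illustration of how capture affects a zero count.** Inputs: 20 participants (Section 6.0). The allocation ratio is not stated in the text; 1:1 is assumed, giving n = 10 active. The share s of affected participants who are captured is assumed.

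Exact two-sided 95% upper limit for 0/n: U = 1 − 0.025^(1/n). For n = 10, U = 1 − 0.6915 = 0.3085, or 30.8%.

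If a share s is captured, the recorded rate is p × s, so the limit on the true rate p is U/s:

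- s = 1: 30.8%, which is due to sample size alone
- s = 0.75: 0.3085/0.75 = 41.1%
- s = 0.50: 0.3085/0.50 = 61.7%

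The chance of recording no event in 10 participants is (1 − p × s)^10:

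- true rate 20%, full capture: 0.80^10 = 10.7%
- true rate 20%, half capture: 0.90^10 = 34.9%
- true rate 10%, full capture: 0.90^10 = 34.9%

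The last two are identical, so a zero count cannot by itself separate a 10% event fully captured from a 20% event half captured.

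**The case against.** The best counter-argument is that capture does exist and that not all of the plan is visible. The trial has one 30-minute exposure in a supervised visit. Staff monitor the session, participants are reminded beforehand that they may stop, burns are watched for, and any adverse event goes to the IRB. Section 10.0 also says "The timeline of the experiment and group assignment overview are displayed below", and that figure is not shown. The visible text goes from Section 10.0 to 12.0, and Section 12.0 says "All data will be stored in the Redcap database as well as in paper documentation" without showing the forms. Any of these may hold an event checklist or vital signs, and the summary statistic may sit in an analysis plan.

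Much of this stands. A reader might infer that the trial collects no safety data, or that a zero count would mean only that nothing prompted a report; Sections 10.0 and 13.0 to 15.0 do not support that. A reader might also infer that vital signs are never taken; the documents support only that the text shown describes no such reading.

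The numerical illustration is not evidence about this trial either. Nothing in the protocol suggests that half of the symptomatic events would go unnoticed, and the figures only show what an assumed capture rate would imply.

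What the counter-argument does not answer is that Section 4.0 leaves the primary safety outcome undefined, and that no visible provision fixes the questions, their timing or equal asking in both arms.

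**Conclusion.** The point holds in a limited form and should be fixed; confidence is medium. Section 4.0 does not define its primary safety outcome, and the visit text shown contains no standard query. The capture that is described is unstandardised and not stated to be the same in both arms. A zero or low count, or a difference between arms, could therefore partly reflect how events were asked about. Separately, the heart-rate and blood-pressure text in Section 15.0 presupposes a means of detection that the visit text does not describe.

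The size cannot be estimated from the documents. Under the assumed 1:1 split, the upper limit for 0/10 runs from 30.8% with full capture to 61.7% with half; the conclusion does not depend on those values. The finding about the visit rests on the visible text and would narrow to the definition in Section 4.0 if the figure, a Section 11.0 or the REDCap forms contain the missing measures.

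**What to change.** 1. In Section 4.0, define the safety outcome as the number of participants per arm with each stimulation-related symptom named in Section 15.0 (local discomfort, soreness or numbness, burn, headache, dizziness, facial pain, fainting), plus any other event elicited by one open question.
2. Ask these from one fixed checklist, worded identically in both arms, before and after stimulation, and add it to the visit sequence in Section 10.0.
3. Reconcile the heart-rate and blood-pressure text in Section 15.0 with the visit procedures. Either list the measurement and its timing, noting that before-and-after readings alone would miss a transient change during stimulation, or state that only symptomatic changes will be detected.
4. Have session completion, any lowering of intensity (Section 10.0) and any change of ear (Section 14.0) recorded and reported by arm as feasibility and tolerability counts. The protocol does not say that they are recorded now.
5. If the timeline figure, a Section 11.0 or the REDCap forms already contain such measures, name them in Section 4.0 instead of adding new ones.

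The cost is a few minutes per visit. Direct questions will also raise the count of mild events in both arms, which should be said when the results are reported.

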Participants will rate their post-stroke upper extremity pain intensity before and after the taVNS using a standard numeric pain rating scale (0-10).

Quantitative Sensory Testing Procedures:

We will measure pain assessments by administering cutaneous stimuli via the Medoc Pathway System (Medoc, Durham, NC) using a 30 x 30 mm ATS thermode. QST will be done using method of limits testing on the thenar eminence of the non-affective forearm (left arm). A program will be set up to administer 5 hot stimuli with random durations between each trial. The ATS thermode begins at 32 deg C and increases by 0.5 deg C per second. Participants will be asked to press a button in order to signify three different measures: (1) sensory threshold, or the temperature at which the stimulus becomes noticeable, (2) pain threshold, or the temperature at which the stimulus becomes painful, and (3) pain tolerance, or the temperature at which the stimulus becomes too painful to tolerate. Measuring these thresholds will yield information about A β , A δ , and C fibers, respectively. The device will be set to stop heating at 51.5° C and stop cooling at 0° C to avoid tissue damage. The QST procedures will be tested before and after the taVNS.

taVNS Procedures:

All stimulation will be conducted using the Sparrow Ascent transcutaneous auricular neuromodulation (tAN) device manufactured by Spark Biomedical (Dallas, TX). These tAN devices are portable, wearable systems that have 2

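### Section 4.0 ties the analgesic effect to a pre-versus-post comparison that names no arm, although Aim 2 asks the question against sham (minor; fixed by wording)

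*Protocol*

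**What the plan says.** Section 4.0 defines two secondary outcomes. For QST it states the comparison: "We will explore the analgesic effects by comparing the pre- and post-intervention QST ratings". For the pain rating it gives an expectation: "We anticipate participants will rate lower pain intensity post-intervention". Neither paragraph mentions active, sham, group or arm.

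Section 1.0 frames the question differently. Aim 2 reads "Investigate whether taVNS can modulate pain in this population compared to sham". The text below it describes the design ("In this single-visit, single-blinded, sham-controlled pilot trial") and plans to compare changes in pain scores and QST pain threshold "before and after a 30-minute taVNS intervention, as well as between active and sham taVNS". Section 3.0 confirms that each participant is randomised to either active or sham stimulation. Section 6.0 sets the sample at 20.

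**The concern.** The section that defines the outcomes attaches the analgesic effect to a contrast that does not answer Aim 2. Aim 2 names both contrasts but does not say which one answers it, so an analyst working from Section 4.0 is directed to the before-after change alone.

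That change mixes any effect of stimulation with whatever else moves the measurements within the visit. Two sources are built into the design: the participant's response to having an intervention at all, and repeated heat testing. On the latter, Section 10.0 says "A program will be set up to administer 5 hot stimuli with random durations between each trial", and the procedure is run both before and after stimulation. Both sources act in both arms, and the sham arm is there to remove them. If the comparison in Section 4.0 is followed as written, a change common to both arms could be reported as analgesia from stimulation when active is no better than sham.

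**Working it through.** **No figure to reproduce.** The protocol gives no test, significance level, SD, allocation ratio or expected non-specific change for these outcomes. What follows illustrates the mechanism only.

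**Input from the protocol:** N = 20 (Section 6.0).

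**Assumed inputs:** two-sided 5% t-tests; normally distributed change scores; 10 per arm; no true active-sham difference; the same beneficial shift δ in both arms, with δ = 0.25, 0.5 or 0.75 SD of within-person change.

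**Step 1. Pre-post test.** The paired t statistic on n participants follows a noncentral t distribution with n − 1 degrees of freedom and noncentrality δ√n. The chance of significance is P(|T| > t(0.975, n − 1)).

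- Pooled, n = 20. This is the literal reading when no arm is named. The critical value is 2.093 and the noncentrality is 0.25√20 = 1.118, 0.5√20 = 2.236 or 0.75√20 = 3.354. The probabilities are 0.186, 0.564 and 0.889, or about **19%, 56% and 89%**.
- Active arm only, n = 10. The critical value is 2.262 and the noncentrality is 0.791, 1.581 or 2.372. The probabilities are 0.109, 0.293 and 0.562, or **11%, 29% and 56%**. With 8 to 12 participants in that arm the ranges are 9-12%, 23-35% and 45-66%.

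**Step 2. Between-arm test.** The mean difference in change is (true effect + δ) − δ, so the shared shift cancels and the test keeps its 5% level whatever δ is. Simulation of 40,000 trials at shared shifts from 0 to 0.8 SD gave 0.049 to 0.052.

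**Step 3. Precision of the contrast that answers Aim 2.**

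- Unadjusted difference in change: half-width of the 95% CI = t(0.975, 18) × √(1/10 + 1/10) = 2.101 × 0.447 = **0.94 SD of change**. With an 8/12 split it is 2.101 × √(1/8 + 1/12) = 0.96.
- Adjusted for baseline, assuming equal pre and post variance and pre-post correlation ρ: the residual variance relative to the variance of change is (1 − ρ²)/[2(1 − ρ)] = (1 + ρ)/2, and chance baseline imbalance adds a factor of 1 + 1/16 on average. The half-width is t(0.975, 17) × √[0.2 × (1 + ρ)/2 × (1 + 1/16)], with t(0.975, 17) = 2.110. This gives **0.84** at ρ = 0.5 and **0.92** at ρ = 0.8.

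**The case against.** The strongest reply is that the protocol already has the right comparison. Aim 2 is posed against sham and plans the active-versus-sham comparison for both pain scores and QST, and nothing says that Section 4.0 replaces it. Section 4.0 mainly describes what is measured and when; the pre-to-post change can be read as the within-person quantity that Aim 2 then compares between arms. The QST sentence only sets out to explore, and the pain-rating sentence is an expectation, not an analysis.

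Much of this stands. A reader might infer that no sham comparison is planned, or that the pre-post change is the formal test of efficacy. The documents support neither: Section 1.0 plans the sham comparison, and no section makes the pre-post change a formal test.

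A reader might also cite the experiment overview line in Section 10.0, which names an anti-pain effect without a comparison. That line cannot be used. It appears to introduce a display of the timeline and group assignment that is missing from the available text, and what the display said about the arms is unknown.

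It is also fair that the percentages do not measure risk in this trial, since no section gives the size or direction of any placebo response or heat adaptation. They also depend on the reading: at 0.5 SD, 56% pooled against 29% in the active arm alone.

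What survives is narrow. The one sentence that says how analgesia will be explored states the uncontrolled contrast, and Aim 2 does not rank its two comparisons. This is not detail that a statistical analysis plan would ordinarily supply: it concerns a sentence the protocol does contain, which such a plan could carry forward.

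**Conclusion.** The point holds as a minor inconsistency. Section 4.0 links the analgesic effect to a before-after comparison with no arm named, while Aim 2 asks about taVNS against sham and leaves open which of its two comparisons gives the answer. With no true effect, a moderate shared shift of 0.5 SD would make a pooled pre-post test significant in about 56% of trials, against 5% for the between-arm test. That figure rests wholly on the assumed shift, the 5% level and normal change scores; the active-arm-only figure (29%) also assumes 10 per arm.

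The weight is limited because the primary outcome is safety and feasibility, the pain outcomes are secondary and exploratory, and Aim 2 already contains the right contrast. What is at stake is a misleading signal for later work, not the trial's primary objective.

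**What to change.** In Section 4.0, state for the pain rating and the QST outcomes that the analgesic effect is the active-minus-sham difference in post-intervention values, adjusted for that outcome's own baseline and given with a 95% CI. Label within-arm pre-post changes as descriptive. In Aim 2, say that the between-arm comparison answers the aim.

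The cost is wording and one degree of freedom for the baseline term, with no new data, visits or participants. Baseline adjustment is the better choice for precision, but the essential change is naming the between-arm contrast. The estimate will remain imprecise at N = 20, as the half-widths above show, so it should be reported as an estimate with its interval and not as a test of efficacy.
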